Most studies regarding language acquisition have focused on understanding when and how infants learn words. It is known that at 24 months, typically developing infants know and produce between 200 and 300 words (Jones & Smith, 2005; MacRoy-Higgins, Shafer, Fahey, & Kaden, 2016) and add to their vocabularies from 22 to 37 words each month (Vuksanovic & Bjekic, 2013). It is also during the first years of life that some principles that promote vocabulary learning are developed. The shape bias, which is a tendency to infer that objects that share the same shape will also share the same name, is the one that has been studied the most. At 24 months, typically developed infants present a shape bias and use it as a strategy to generalize words (Jones, 2003; Weismer, Venker, Evans, & Jones Moyle, 2013). In contrast, Late Talkers do not exhibit this preference and present a difficulty in organizing objects by shape (Jones, 2003). It has also been found that teaching typically developed infants a shape bias before the end of the second year of life boosts their vocabulary development (Smith, Jones, Landau, Gershkoff-Stowe, & Samuelson, 2002). Despite this, the possibility of teaching Late Talkers this principle and its effect on their vocabulary and language development has not been explored.

1.1. The shape bias in typical language development

During the first years of life, infants learn and produce mainly words related to object names. Several studies have suggested that between 18 and 24 months, infants learn that novel words can be generalized or extended on the basis of visual properties, especially on the basis of shape, which is known as the ‘shape bias’ (Borgström, Torkildsen, & Lindgren, 2015; Landau, Smith, & Jones, 1998; Perry & Samuelson, 2011). This bias is a tendency to extend names to objects that share the same shape and not other visual properties such as colour, texture or size (Dansereau, 2016; Hupp, 2015). For example, two round objects can be called “ball” because of their shape even if both objects have different colours, sizes or textures. A shape bias is a useful strategy because object categories tend to be organised by shape (Graham, Williams, & Huber, 1999) and shape is a perceptual feature that can be identified quicker than other visual properties (Landau, Smith, & Jones, 1988).

1.2. The shape bias in Late Talkers

Late Talkers are infants that show a limited expressive language characterized by less than 50 words by the age of 2 in the absence of a physiological, cognitive or genetic disorder that may

account for this delay (Macroy-Higgins & Montemarano, 2015; Rescorla, 2011; Weismer et al., 2013). Late Talkers tend to be below the 15th percentile of expressive vocabulary (Colunga & Smith, 2008) and represent from 10% to 15% of the total infant population (Tsybina & Eriks-Brophy, 2007). Some of these infants “catch up”, but others show persistent language difficulties throughout their lives.

Interestingly, Late Talkers do not exhibit a shape bias (Colunga & Sims, 2011; Weismer et al., 2013). This might contribute to their language delay and to their difficulty of adding new words to their vocabulary, even though this is unlikely the only cause of their language delay. A family history of language delay and limited interaction between parent/guardian and infant are likely other important factors (Girolametto, Weitzman, & Earle, 2013).

The three conventional approaches followed for Late Talkers are ‘wait and see’, ‘watch and see’, and ‘early intervention’. The ‘wait and see’ approach means no action or intervention, and it is advised to wait until the infant is older to see whether a language delay is indeed present (Girolametto et al., 2013). The ‘watch and see’ approach consist of monitoring the infant’s language development and evaluate it every 3 to 6 months (Preston et al., 2010) to assess if intervention is required or if the infant “catches up”. The ‘early intervention’ approach consists of actively working with the infant to help them to develop their language.

The typical intervention for Late Talkers consists of a series of meetings with a speech and language therapist in group or individual sessions providing language and communication stimulation as well as providing parents and guardians with ideas for how to support their children’s language development at home. Most of these interventions tend to include techniques such as focused stimulation, modelling target words (Cable & Domsch, 2011), general language stimulation and milieu teaching (Finestack & Fey, 2013). For focused stimulation, the parent or carer establishes a joint focus with the child by producing an object’s name (e.g. “ball”), a comment (e.g. “Look!”) or a two-word utterance (e.g. “big ball”) (Cable & Domsch, 2011). The technique of modelling target words consist of repeatedly mentioning words to the child in an informal, play-like context (Cable & Domsch, 2011). The general language stimulation technique consists of creating a rich environment in which the child can experience different objects and activities (Finestack & Fey, 2013) such as reading books, playing, helping in everyday activities, etc. Finally, the milieu teaching consists of identifying specific goals and, with the use of naturalistic settings or activities, encourage the child to attempt to use target words or behaviours (Finestack & Fey, 2013). Considering these techniques used in Late Talkers interventions, it appears that many of them aim at teaching the infants specific words or communication patterns they do not know.

1.3. The shape bias as a strategy to boost vocabulary acquisition

Besides being a characteristic of typical language development, evidence suggests that very young typically developing infants that do not have a shape bias yet can be taught to use it as a cue to generalize novel labels, and importantly, that this can have a positive effect on their general word learning. A study by Smith et al. (2002) showed that 17-month-olds can be taught to generalize names to objects that share the same shape. During 7 weeks, infants were presented with sets of novel objects with novel names based on the objects' shape. After this training phase, infants extended the names of both the trained and completely new unfamiliar objects on the basis of shape. Importantly, using a vocabulary checklist filled in by the infants' parents, the study also found that the infants' vocabulary had grown significantly faster over the course of the intervention than that of a control group of infants who did not receive the intervention.

2. The present study

Given the evidence of the benefits of teaching infants a shape bias for their language development and the lack of a shape bias in Late Talkers, the present study will assess if Late Talkers can be taught a shape bias and benefit from it in their vocabulary and language development. Such an intervention can potentially function as a powerful alternative to teaching children specific words. Considering the positive results obtained by Smith et al. (2002) with typically developing children, this intervention programme might help Late Talkers develop a useful attention bias for word learning.

3. Research Questions

3.1. Primary objectives

The main objectives of the present study are:

- A. To investigate whether it is possible to teach Late Talkers to attend to objects' shapes as a useful property for learning and generalizing novel object labels.
- B. To assess the benefits that this intervention programme has on Late Talkers' short-term vocabulary development compared to an intervention where infants will be taught specific words ('specific word' intervention).
- C. To assess the benefits of the intervention programme on language and cognitive development one year after the intervention compared to the 'specific word' intervention.

3.2. Secondary objectives

As a secondary objective, the study will investigate whether some children are more receptive to the shape bias intervention programme than others. More specifically, we will:

- D. Assess whether the success of teaching Late Talkers a shape bias for noun extension is related to their sensitivity to object shape similarities.
- E. Assess whether the success of teaching Late Talkers a shape bias for noun extension is related to their ability of sustain their attention to novel objects that are presented to them.

3.3. Primary outcome measures

Objective A), i.e. whether children have learned a shape bias, will be assessed by means of a noun extension test with novel names and objects never heard and seen before by the infants at the end of the intervention programme.

Objective B), i.e. whether the intervention programme benefits infants' general vocabulary development, will be assessed with a vocabulary checklist filled in by the parents/guardians before and after both types of intervention. We will compare the vocabulary growth in the group of children that took part in the shape bias intervention programme with that of the group of children that took part in the 'specific word' intervention. A significant larger increase in the shape bias intervention compared to the 'specific word' intervention will provide information regarding the success or efficacy of the shape bias intervention.

Objective C), i.e. whether the shape bias intervention has a "long-term" effect on language development and cognitive abilities. Receptive and expressive language, and cognitive abilities, such as visual spatial skills and working memory, will be assessed at one year after the end of the intervention programme.

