4.3. Tests and procedure of intervention programme

4.3.1. Vocabulary and developmental assessments. At session 1, parents/guardians will fill in a socioeconomic and general development questionnaire (see Appendix 1.5). The

information provided in this questionnaire will double-check the inclusion/exclusion criteria. It will also be used to check whether the intervention was only successful in a sub-group of the infants (e.g. those without a family history of language problems). In the first and last session, parents/guardians will also be asked to fill in the UK-CDI Words and Gestures questionnaire, a vocabulary checklist of words and phrases that infants might know and use (Alcock, Meints, & Rowland, 2017; see Appendix 1.4). This will allow us to compare language development during the intervention programme between the two intervention groups.

4.3.2. Initial cognitive assessments: The initial cognitive assessments will be presented during the first two sessions. During week 1, infants will be assessed with a shape sorting task and an attention task. The sorting task will last no more than 5 minutes and will be used to assess if before the training programme, infants are sensitive to the shape of objects and can group objects by shape. Infants will be presented with 16 novel objects differing in shape, colour and texture and asked to sort them into groups. How to sort (namely by shape) will be shown to them with the means of examples. The attention task will last 3 minutes and will assess infants' joint and sustained attention. This will be achieved by monitoring their eye movements during the presentation of five short video clips (35 seconds each) of a person looking at and moving unusual novel objects. For this task, participants will sit on their parent/guardian's lap in front of a computer screen. Eye movement will be monitored with a remote eye tracker (see Figure 2). The parent will wear blacked-out glasses so that their behaviour cannot affect the infants' eye gazes.

At week 2, infants' visual spatial abilities and working memory will be assessed using the Wechsler Preschool & Primary Scale of Intelligence - Fourth UK Edition (WPPSI-IV UK). This test will last about 20 minutes and will be used to rule out any potential cognitive delay.

Figure 2. Attention task. Infants will watch five short videos and eye movements will be monitored with a remote eye tracker.

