4.4. Procedure of follow up study

A follow up study will be conducted one year after the start of the intervention programme in order to assess the long-term effects of the intervention in language and cognitive development. For this follow up study children's language, and cognitive abilities, will be assessed. The British Picture Vocabulary Scale (BPVS3) will be used to assess receptive language. In this test the child will listen to a word and will have to select from a set of pictures, the image that corresponds to that word. The Wechsler Preschool & Primary Scale of Intelligence - Fourth UK Edition (WPPSI-IV UK) will be used to assess infant's visual spatial skills and working memory. In this test, the child will be asked to recreate different figures using blocks and to view animal cards on a zoo layout for a specified time, remember where they are located, and then place each card in the previously viewed location.

5. Ethical considerations

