6.3.2 Primary outcome analysis

During weeks 8 and 9 of the study infants will be assessed with two forced choice tasks where they will have to extend object names to new exemplars based on visual commonalities. We will assess the statistical difference between the response pattern and chance (using t-tests). This will show whether infants have learned to extend object names by shape similarities. The factors that predict the number of noun extensions based on shape as well as vocabulary growth will be assessed using mixed effect model analyses. The most important factors tested in the models will be the number of words known before the intervention, the intervention type (shape training vs specific word training), attention measures (pre-test and attention during training), and sorting task measure. The outcome of these analyses will show whether the shape bias intervention has led to a larger vocabulary growth than the specific word intervention (as a control intervention). It will also assess the role of attention in word learning and whether only infants that pay attention to novel items

presented to them or infants that are sensitive to shape similarities between objects can acquire a shape bias. Only data of infants that complete the intervention will be analysed.

Regarding the follow up study, infants' vocabulary and cognitive abilities will be assessed. This with the aim of analysing if there are any long-term effects of each intervention and infants continue learning words and potentially "catching up", or if the intervention programmes are only beneficial while they are being implemented. The cognitive assessments will be used to assess whether the intervention has an effect on visual spatial skills and working memory. In both cases, it will be done by comparing the infants results to the standardized mean of UK infant population. Similarly, infant's result in the follow up language assessment will be compared to the standarized mean of UK infant population.

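### Section 3.3 names expressive language as a one-year primary outcome, but the follow-up in section 4.4 schedules no expressive measure

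*Combined protocol and SAP*

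**What the plan says.** Objective C is one of three primary objectives. Section 3.1 words it broadly: "To assess the benefits of the intervention programme on language and cognitive development one year after the intervention compared to the 'specific word' intervention". Section 3.3, which sets the primary outcome measures, is more specific and names both language domains: "Receptive and expressive language, and cognitive abilities, such as visual spatial skills and working memory, will be assessed at one year".

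Section 4.4 sets out the follow-up visit. On language it says: "The British Picture Vocabulary Scale (BPVS3) will be used to assess receptive language". It then describes how the child responds: "In this test the child will listen to a word and will have to select from a set of pictures". The only other instrument, the WPPSI-IV UK, "will be used to assess infant's visual spatial skills and working memory".

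The vocabulary checklist belongs to the intervention period. Section 4.3.1 says: "In the first and last session, parents/guardians will also be asked to fill in the UK-CDI Words and Gestures questionnaire". Section 6.3.1 (item A) confirms that it yields two counts, words understood and words produced, before and after the programme.

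Section 6.3.2 says the follow-up is meant to show "if there are any long-term effects of each intervention and infants continue learning words and potentially 'catching up". It does this by comparing the follow-up language result with the UK standardised mean. Section 1.2 gives the condition its definition: "Late Talkers are infants that show a limited expressive language characterized by less than 50 words by the age of 2".

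**The concern.** A primary outcome is named and no instrument is assigned to it. The gap will not close by itself: section 5.7 requires the protocol to be followed strictly and rules out planned deviations, so a researcher working from 4.4 will collect no expressive data at one year. A one-year measurement that is not taken cannot be recovered later.

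Two things are at stake. The report could not present an outcome that 3.3 lists as primary. And the question in 6.3.2 about catching up would be answered with a comprehension test, in children whose condition the background section describes in terms of production. Whether any gain in words produced seen at the end of the programme lasts to one year could not be examined.

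**Working it through.** No figure in the plan bears on this point. The sample size in section 6.1 does not enter, so the check is a comparison of the text.

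| Question | Section | Receptive language | Expressive language |
|---|---|---|---|
| Named as a one-year primary outcome? | 3.3 | Yes | Yes |
| Instrument at first session | 4.3.1, 6.3.1 A | UK-CDI, words understood | UK-CDI, words produced |
| Instrument at last session | 4.3.1, 6.3.1 A | UK-CDI, words understood | UK-CDI, words produced |
| Instrument at one year | 4.4 | BPVS3 | None |
| Analysis at one year | 6.3.2 | Comparison with UK mean | None possible |

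1. Language domains named for one year: 2. Domains with an instrument at one year: 1. Domains without: 2 − 1 = 1, the expressive one.
2. The BPVS3 cannot fill the gap. Section 4.4 labels it receptive, and the child picks a picture for a word that is heard. No word has to be produced.
3. The WPPSI-IV cannot fill it either. In 4.4 it consists of rebuilding figures with blocks and placing cards from memory.
4. The UK-CDI could supply words produced, but neither 4.3.1 nor 6.3.1 places it after the last intervention session, and 4.4 does not mention it.
5. Figure 1 was not available for this check. Its caption refers to the timeline of the intervention programmes, and 4.4 describes the follow-up in text, so it is unlikely to hold a further test.
6. The BPVS3 is not among the baseline assessments in 4.3. A one-year score can therefore be set against the norm, but not against the same child's starting point on that test.
7. Age at follow-up, which matters for the remedy: entry is at 24 to 48 months (4.1.1). Adding 12 months gives 24 + 12 = 36 to 48 + 12 = 60 months, so about 3 to 5 years. Section 3.3 counts the year from the end of the programme and 4.4 from its start. With nine weekly sessions this shifts the range by about two months and does not alter the conclusion.

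**The case against.** The strongest reply is that Objective C is under-measured, not unmeasured. Section 3.1 speaks only of language and cognition, and receptive vocabulary, visual spatial skills and working memory are all collected at one year. The word expressive appears only in the 3.3 outcome sentence, and removing it is an edit of wording. Objectives A and B are untouched. This is fair, and it bears on how much is lost. It does not remove the conflict, because 3.3 is where the primary outcomes are specified.

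The reply is also right against several stronger readings that a reader might infer:

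- That word production is what the intervention targets. Not supported. Objective A concerns generalising labels, tested by asking the child to show an object (4.3.4, 4.3.5), and vocabulary is recorded as words understood as well as words produced (6.3.1 A). Receptive vocabulary is a relevant one-year outcome.
- That receptive language lies outside the enrolled children's delay. Not supported. Sections 4.1 and 4.1.1 require a moderate or severe language delay with no domain stated; the expressive description comes from the background in 1.2.
- That children will score near the receptive norm at one year, or already did at entry. The documents give no receptive profile for this sample. It is possible, but it is an assumption.
- That the plan would declare such a score to be catch-up. Section 6.3.2 states a hedged aim and a comparison with the UK mean. It sets no decision rule.

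**Conclusion.** The point holds as a conflict between sections. Section 3.3 commits to expressive language as a one-year primary outcome, and nothing in 4.4 or elsewhere provides for measuring it. One of two named language domains would have no data, whatever number of children attend the follow-up. The catching-up aim in 6.3.2 would rest on receptive vocabulary alone. That can inform whether children go on learning words, but it cannot show whether they have caught up in production.

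The conclusion rests on the text alone, on 4.4 being the complete list of follow-up instruments, and on Figure 1 not adding one. It does not depend on any assumption about the children's receptive scores. It does not extend to saying that Objective C as a whole goes unmeasured, or that a false claim of catch-up is built into the analysis.

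**What to change.** Reconcile 3.3, 4.4 and 6.3.2 before follow-up visits begin, by one of two routes.

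(a) Add a parent-completed expressive measure to 4.4. The UK-CDI words-produced count is the obvious candidate because it is already collected at the first and last sessions. State the analysis in 6.3.2: words produced at one year compared between arms, with baseline words produced as covariate. Report by arm how many children reach the top of the list. The comparison between arms is what Objective C in 3.1 asks for, and it does not rely on norms, which the reference list gives as preliminary for this instrument. The cost is one extra form, an amendment under section 5.8, and a real possibility of a ceiling, since children will be about 3 to 5 years old and the documents give no evidence that the checklist suits that age.

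(b) Delete the expressive outcome for Objective C from 3.3, and limit the one-year language conclusion in 6.3.2 to receptive vocabulary, with no claim of expressive catch-up. The cost is wording only, again by amendment, and a narrower claim.

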3.4. Secondary outcome measures

Objective D), i.e. whether children are more receptive to the shape bias intervention if they are sensitive to shape similarities, will be assessed by relating children's ability to sort objects by shape before the intervention and their ability to extend object labels by shape after the intervention.

Objective E), i.e. whether children' are more receptive to the shape bias intervention if they can sustain their attention to novel objects, will be assessed by relating children's sustained attention during the presentation of a video showing a person presenting and moving novel objects before the intervention, their attention to the novel objects during the intervention, and their ability to extend object labels by shape after the intervention.

4. Method

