4.2. Study design

Infants will be randomly allocated to one of two groups: shape training group or specific word training group. Over a series of 9 weekly sessions, all infants will be assessed on different tasks that can be divided into 5 stages: Vocabulary and developmental assessments, initial cognitive assessments, training sessions, first-order generalization test, higher-order generalization test. Depending on the group that the children will be in, they will receive either a shape training or a specific word training. Other assessments (initial assessments, cognitive assessments, first-order generalization test and higher-order generalization test) will be identical across the groups. Additionally, a follow up study will be conducted after one year of completion of the intervention programme. A table describing the intervention procedure is provided in Figure 1. Details of the tasks are given below.

[figure not shown]

Figure 1. Timeline of intervention programmes.

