4.3.3. Training sessions

4.3.3.1. Shape training: During the first seven weeks, infants will be presented with four novel words paired with four novel sets of objects (total duration 15 minutes). Each set will consist of two exemplars with the same shape but with different colours and textures. Each set will be presented with sentences such as “*Look! It is a kiv. Do you want to play with the kiv?, Let’s play with the kiv*”. Half way through the presentation of the exemplars, the researcher will bring out a third contrasting object. This contrasting object will be presented with the sentence “*Oh no, this is not a kiv*” and will be taken away immediately. The other three sets of novel exemplars will be presented in the same manner.

4.3.3.2. ‘Specific word’ training: This training will resemble a typical word learning intervention. During the first seven weeks infants will be introduced to 28 real common objects and their names (e.g. biscuit, trousers, slide), randomly divided into 7 sets of four words. During each session, infants will be presented with one of the sets and each session will have a total duration of 15 minutes. The target words have been selected from the Wordbank database, an open database that lists the proportion of children that know a specific word at a specific age. Twenty-eight words that 80% of the total child population at 25 months know were randomly selected as target words. Each session will consist of a 15 min play session in which each object name will be presented at least 10 times and each object name will be mentioned at least 10 times. Additionally, techniques such as focused stimulation and modelling target words, which have proved to be useful for word learning, will be used.

4.3.4. First-order generalization: At week 8 infants in both groups will be assessed as to whether they have learned that objects that have the same shape share the same name. They will be presented with each exemplar used during the training sessions accompanied by three novel toys. These three objects will share only one visual property with the training objects (colour, shape or texture). The three objects will be placed on a table and the researcher will say “*This is a kiv, Can you show me the other kiv?*” while he/she shows the infant one of the exemplars used during the 7 training weeks. All infants will be tested on each trained object with the same procedure. This test will last 8 minutes.

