6.3.1 Summary of baseline data

From the total number of assessments and tasks, results from five of them will be used as baseline data or descriptive statistics. These five assessments are: Vocabulary checklist, Socioeconomic and general development questionnaire, attention task, sorting task, initial working memory assessment, and initial visual spatial abilities assessment. The description of the variables analysed on each assessment and how they will be reported is as follows.

- A. Vocabulary assessment: Parents will fill out this checklist before (and after) the intervention and the total number of words that the infant understands and the total number of words they

produce will be registered as continuous variables and will be considered as the baseline language ability before the intervention programme.

- B. Socioeconomic and general development questionnaire: This questionnaire will provide information regarding general child development, language delay family history, and family status. A number of different types of variables will be collected: nominal variables (e.g. occupation) and ordinal variables (e.g. infant's order of birth). These variables will be used for descriptive statistics. They are potentially interesting as predictor variables, but the sample size is likely too small to draw any strong conclusions.
- C. Attention measure: With this measure, we will assess the fixation duration (number of milliseconds an infant looks) towards a novel object that is moved. The object will be moved for 25 seconds (25000 ms) and the infant's total looking time towards the screen will be registered. This variable will be registered as a continuous variable and used as a predictor of the primary outcome measures.
- D. Sorting task: This will be registered as a categorical variable. Infants will sort objects and depending on their sorting tendency they will be assigned to one of four categories: preference for shape, preference for colour, preference for texture, no preference. This variable will be used as a predictor of the primary outcome measures.

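### Objective E asks who is receptive to the shape programme, but 6.3.2 lists attention during training in two-arm models with no attention-by-intervention term, and the text describes no recording of it

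*Combined protocol and SAP*

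**What the plan says.** All references are to the combined protocol and SAP.

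- **The question.** Section 3.2 states Objective E as: "Assess whether the success of teaching Late Talkers a shape bias for noun extension is related to their ability of sustain their attention". Section 3.4 words it as receptiveness to the shape bias intervention.
- **The measures.** Section 3.4 relates three things: sustained attention to a video before the intervention, then "their attention to the novel objects during the intervention, and their ability to extend object labels by shape after the intervention".
- **The analysis.** Section 6.3.2 names among the most important model factors "attention measures (pre-test and attention during training), and sorting task measure". Intervention type, shape training against specific word training, is in the same list, so the models cover both arms. The outcomes are shape-based noun extensions and vocabulary growth. Section 6.3.3 refers back to this model and mentions a single attention measure.
- **How attention is measured.** Section 4.3.2 gives one procedure: "During week 1, infants will be assessed with a shape sorting task and an attention task". Section 6.3.1 item C defines one variable, from that video: "The object will be moved for 25 seconds (25000 ms) and the infant's total looking time towards the screen will be registered".
- **What happens in training.** Section 4.2 lists the stages as "Vocabulary and developmental assessments, initial cognitive assessments, training sessions, first-order generalization test, higher-order generalization test". Section 4.3.3 describes content and duration for both arms. The shape arm plays with sets of novel objects. In the specific-word arm, "infants will be introduced to 28 real common objects and their names".

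**The concern.** Two gaps meet here. First, a predictor that 3.4 and 6.3.2 both rely on has no described recording method, score or unit. Second, its definition in 3.4 refers to novel objects, which only one arm sees in training, while 6.3.2 lists it for models of both arms.

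The second gap matters more for inference. Receptiveness to the shape programme can be shown only by children who receive it. One attention slope fitted to everyone averages that relation with a different one: attention to familiar objects, in children who were never taught shape, against their shape choices. A null result could then hide a real relation in the shape arm, and a positive result could come from the control arm. If training attention is instead left missing for control children, any complete-case model containing it loses that whole arm and can no longer estimate the intervention effect.

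Attention in live sessions cannot be recovered later if it was not recorded. The scoring and the analysis set would otherwise be chosen after the data are seen.

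**Working it through.** **1. Is the training measure described anywhere?** The stage list in 4.2, the assessments in 4.3.1 and 4.3.2, the training in 4.3.3, the tests in 4.3.4 and 4.3.5, and the variable definitions in 6.3.1 yield one attention variable, looking time in the week-1 video. None of them describes a score, observer coding or eye tracking during training.

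**2. Does it apply in both arms?** As worded in 3.4 (the novel objects), it applies to the shape arm only. As worded in 6.3.2 (attention during training), it could be scored in both arms, but to different objects.

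**3. What does a common slope estimate?** With arm in the model, equal arms and equal spread of attention within arms, the common slope is the average of the two arm slopes:

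(shape-arm slope + control slope) / 2

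Take unit residual variance and a shape-arm correlation r, so that the shape-arm slope is r / √(1 − r²). The values of r are assumptions; the plan gives none.

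| r | Shape-arm slope | Common slope, control slope 0 |
|---|---|---|
| 0.5 | 0.5 / 0.866 = 0.58 | 0.29 |
| 0.6 | 0.6 / 0.8 = 0.75 | 0.375 |
| 0.7 | 0.7 / 0.714 = 0.98 | 0.49 |

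Simulation gave mean common slopes of 0.29, 0.37 and 0.49. With other allocations the factor is the shape arm's share: 10 of 24 gives 0.42, and 14 of 24 gives 0.58.

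**4. Does pooling cost power?** That depends on the control slope, which is unknown. Simulated power at r = 0.5, with 12 per arm and two-sided 0.05 (shape-arm-only figures differ between rows by simulation error):

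| Control slope | Common slope | Shape arm only |
|---|---|---|
| 0 | 24% | 38% |
| half the shape-arm slope | 47% | 41% |
| equal to it | 70% | 39% |

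If the relation exists only in the control arm, with r = 0.5, 0.6 or 0.7 there, the common slope is significant in 24%, 35% and 48% of trials.

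**5. What can the shape arm support?** Section 6.1 plans for 24 completers out of 30 recruited. At 1:1 that is 12 shape-arm children, or 15 if all finish. By Fisher's z, the smallest correlation detectable with 80% power at two-sided 0.05 is tanh[(1.960 + 0.842) / √(n − 3)]:

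- n = 12: tanh(2.802 / 3) = 0.73
- n = 15: tanh(2.802 / 3.464) = 0.67
- n = 24, both arms: tanh(2.802 / 4.583) = 0.55

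The 24 in 6.1 is not tied to Objective E, and nothing here depends on reproducing it.

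**The case against.** - **The plan clearly intends to collect the measure.** It is named in both 3.4 and 6.3.2. Figure 1 and the appendices could not be seen. A reader might infer that no session measures attention, or that the variable does not exist. The documents do not support that. What can be said is that the text describes no recording, and 4.2 does say that the task details follow in the text.
- **Each section is coherent alone.** The wording in 3.4 naturally describes shape-arm children, and 6.3.2 can mean attention to whatever is being trained. This stands, but the two then differ, and the plan does not say which is modelled in whom.
- **6.3.2 gives factors, not an equation.** It does not exclude an interaction or a shape-arm analysis. This also stands: the common slope is the plain reading of a list of factors, not a stated model. Nor is keeping both arms the problem. With an interaction term, power for the shape-arm slope at r = 0.5 is about 42% with control slope 0, slightly above the shape-arm-only analysis.
- **Pooling need not lose power.** This stands in full. The loss appears only when the control slope is near zero; at equal slopes pooling gains a good deal. Power is therefore not the ground for the change.
- **The week-1 measure exists in both arms**, so Objective E remains partly answerable. That is right, but a common slope on that measure also includes children never taught shape, so the same restriction is needed there.

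**Conclusion.** The point holds as a mismatch between question and analysis. Objective E concerns response to the shape programme, while the analysis as listed has no term that isolates it, and one of its two attention measures has no described recording and no meaning, as 3.4 defines it, in the specific-word arm. The common slope is about half the shape-arm slope if attention matters only in that arm. This assumes 1:1 allocation, which 4.2 does not state, and equal spread of attention in the arms. It equals the shape-arm slope if the two arms share a slope.

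A reader might infer that the variable is undefined in half the sample, that pooling always costs power, or that Objective E cannot be answered. The first needs an allocation ratio that the plan does not give, the second fails once the control slope is appreciable, and the third ignores the week-1 measure. The point affects one secondary objective and is worth correcting because the correction is nearly free.

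**What to change.** **Analysis (6.3.2 and 6.3.3).** State that Objective E is answered by the slope, in the shape arm, of the week-9 shape score on attention. Take it from an attention-by-intervention interaction or from a shape-arm-only model. Apply this to both the week-1 video measure and the training measure, report it with a confidence interval, and label it exploratory (about 12 to 15 children if allocation is 1:1). If training attention is scored only in the shape arm, use the shape-arm-only model for it and keep it out of models covering both arms.

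**Measurement (4.3.3.1).** State a simple attention score for each of the four novel sets in each session, recorded by the researcher already present. An attended-or-not score may vary little in one-to-one play, so check it for spread early or use a short graded scale.

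**If no score will be taken.** Delete attention during training from 3.4 and 6.3.2, and answer Objective E from the shape-arm slope on the week-1 measure.

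**Cost.** One tally per session, or nothing if the term is deleted. The statistical price is a wider interval than pooling would give if the slopes are in fact equal in the two arms.
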